# → if no: Where does the one you care for live?

#### (Please tick one box only)

-	Lives with spouse
-	Lives with other family
*	Lives alone
*	Nursing home
.	Other:

# 7: Does the person you care for need any help in one of the following areas? If yes, is he/she partly or completely reliant on the help of others?

(Please cross one number for each line)

	Completely dependent	Partly dependent	No need for help
For health reasons: (e.g. medication intake, medical treatment, rehabilitation, therapy, etc.)	t	ł	H
For constitutional/ personal reasons: (e.g. washing oneself, dressing oneself, eating or going to the toilet)	ŧ		
For mobility reasons: (e.g. at home or outside of the home, transport-related)	Ť	ŧ	ŧ
For emotional/psychological/social reasons: (e.g. keeping company, giving the feeling of security, calming down)	Ŷ	ŧ	ł
In the household: (e.g. homework, transport)	Ť	ŧ	٠
For the organisation of finances: (e.g. helping to pay bills from the PATIENT's money)	Ť	ŧ	٠
For financial reasons: (e.g. by financial support / paying bills for the patient from OWN money)	Ŷ	٠	
Organisation of care: (e.g. taking up the contact to care providers)	ŧ		۲

#### 8: How long have you been providing care for the person you care for?

(Please enter the exact number of years and months. If you don't remember the exact number please try to estimate)

Years |\_\_||\_\_| Months ||\_\_||\_\_|

# 9: How many hours per week do you provide assistance, care, supervision or companionship to the person you care for?

(Please enter the exact number of hours per week. If you don't remember the exact number please try to estimate)

Hours per week |\_\_||\_\_|

#### 10: Has your employment status changed as a result of your caregiving duties?

(Please tick one box only)

- ▶ No  $\rightarrow$  if no: go to question X7
- Yes → if yes: what has changed in your employment?
  - Early retirement
  - Changed jobs
  - Began working
  - Family leave
  - 🕳 Quit job
  - Leave of absence
  - 🛓 Laid off
  - Increased hours
  - Decreased hours
  - Other: \_\_\_\_\_

# 11: Do you sometimes wish for more social support from friends and family in order to manage the caregiving tasks?

- .
- No

Yes

......

# 6.14 Annex 10 – Interview guides (English sample draft)

## Interview guide for patients finishing the intervention period

	First priority questions	Area to cover
Opening question	1 Please describe your overall experienced with SENACA?	Overall experience
	 Please describe your use of computers, mobile devices or other modern electronics in relation to health before the intervention	Prior ICT experience
Initial experience	3 Describe your thoughts about SENACA when you first heard about it	Technology readiness
	4 Please elaborate on the introduction session given in advance	SENACA improvements
Experiences	5 Please describe some factors that made it easier for you to use the program	Facilitators/barriers
Experiences	6 Please elaborate on positive experiences produced by using SENACA	Facilitators/barriers
	7 Please describe your use of the different elements in SENACA - which one did you find most useful?	SENACA improvements, eHealth literacy
	8 Please describe the assistance you got from other people e.g. family in order to use SENACA	Age barriers
The specific use	Please elaborate on your health behaviour in terms of physical activity, alcohol consumption etc. during the SENACA period	Behaviour change
	10 Please elaborate on your level of involvement in managing your health during the SENACA period	Self-management
Future	11 From your perspective what modules, elements etc. should be changed in SENACA in order to improve it?	SENACA improvements
	Second priority questions	
	How did you experience the technical support in situations of technical problems?	SENACA improvements
	Pleace describe your thougths about having your healt data on a computer software	Data security
	Describe how SENACA did influence your feeling of indendence of other people, family members etc.	Autonomy
	Please elaborate on your experiences related to the interaction with other people using SENACA (the forum)	Self-management
	Please describe your use of healthcare services during the study period	Healt care utilization
	Please describe your expectation of using electronic or online tools in relation to your illness in the future	Usability and older adults

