#### 2.2.8 Data analysis

Explorative and descriptive data analyses will mainly be performed in this field-test study with a relatively small sample size.

First, descriptive analysis on usability will give a general overview of how users, both informal carers and patients, view SENACA before having used it. The findings will be compared with perceived usability after having experienced it for the whole intervention period (up to day 100). This will provide insights on practical implications on the design and introduction of SENACA. A qualitative analysis on break-offs and non-response further completes the findings by exploring the barriers and drivers of usage. In addition to that, the usage of the several components of SENACA will be compared regarding frequency and intensity to explore which aspects are more or less accepted by the user groups.

In a second step, the clinical and behavioural parameters and quality of life will be screened at baseline measurement. This initial description gives further insights into the characteristics of the sample. Changes in parameters over time will be explored to gain insight into the functionality of SENACA.

Overall, mean values will be compared on the basis of non-parametric tests to identify significant differences between groups. Even though the study does not meet the requirements of an experimental design, the ex-ante and ex post measurement allows monitoring changes of the observed variables. Bias due to non-observable errors may be possible.

Data from qualitative study parts (i.e. interview transcripts, content from open-ended questions or user forums) will be coded applying thematic analysis (Bradley, Curry & Devers, 2007) in order to categorize the data as well as to identify patterns leading to a nuanced evaluation of the usability of SENACA from a technological, educational and behaviour perspective. The qualitative analysis will be guided by taxonomies and frameworks on the subject of matter to be used as sensitizing concepts, for instance Michie et al. (2013) or Greenhalgh et al.(2015). Computer-aided qualitative data analysis (most likely MaxQDA®) will be used for coding and synthesising the findings.

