### Interview guide for the drop-outs

	First priority questions	Area to cover
Opening question	1 Please describe your overall experience with SENACA?	Overall experience
	2 Please describe your use of computers, mobile devices or other modern electronics in relation to health b using SENACA	Prior ICT experience
Initial experience	3 Describe your thoughts about SENACA when you first heard about it	Technology readiness
	4 Please elaborate on the introduction session giving in advance	SENACA improvements
5 (	5 Please describe the reason(s) why you withdraw from using SENACA?	Facilitators/barriers
Reasons for withdrawing	6 Please elaborate on positive (or negative) experiences produced by using SENACA	Facilitators/barriers
	7 Please describe barriers for you using the program	Facilitators/barriers
Future	8 From your perspective what should be changed in SENACA in order for you to use SENACA?	SENACA improvements
	Second priority questions	
	How did you experience the technical support in situations of technical problems?	SENACA improvements
	Pleace describe your thougths about having your healt data on a computer software	Data security
	Please elaborate on your health behaviour in terms of physical activity, alcohol consumption etc. during th SENACA period	e Behaviour change
	Please elaborate on your level of involvement in managing your health during the SENACA period	Self-management
	Please describe your use of the different elements in SENACA - which one did you find most useful?	SENACA improvements, eHealth literacy
	Please elaborate on your experiences related to the interaction with other people using SENACA (the form	um) Self-management

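### Under the shared area Facilitators/barriers, the Annex 10 interview guides prompt completers only for helpful factors and good experiences and give the direct barrier prompt only to drop-outs, so barriers among completers and drivers among drop-outs may be under-elicited.

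*Protocol*

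**What the plan says.** Section 2.2.6 (Interviews) invites both those who finish the programme and those who discontinue to a semi-structured phone interview with open-ended questions. Section 2.2.8 states one purpose: "A qualitative analysis on break-offs and non-response further completes the findings by exploring the barriers and drivers of usage". The patient guides are in Annex 10, section 6.14, which is marked as an English sample draft. Each question there carries a label for the area it is meant to cover.

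In the guide for patients who finish, two first-priority questions carry the label Facilitators/barriers:
- item 5: "Please describe some factors that made it easier for you to use the program"
- item 6: "Please elaborate on positive experiences produced by using SENACA"

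In the guide for drop-outs, three first-priority questions carry that label:
- item 5, on why the person withdrew
- item 6: "Please elaborate on positive (or negative) experiences produced by using SENACA"
- item 7: "Please describe barriers for you using the program"

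**The concern.** The label promises both halves, facilitators and barriers, but each guide prompts directly for only part of it, and which part depends on whether the person stopped. Item 6 shows this most clearly: the question is the same in both guides, except that only the drop-out version opens the door to negative experiences.

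Two things are at stake. First, people who persisted may have met obstacles and found ways round them. Section 2.3 wants to identify features of the prototype to optimise, and those accounts serve that aim well, yet nothing in the completer guide asks for them directly. Second, drop-outs may have had reasons to use the system before they stopped, and nothing in their guide asks directly what helped. If a report then sets the themes from the two groups side by side, some of the difference will come from what each group was asked.

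**Working it through.** No arithmetic beyond counting applies. The check compares the two guides item by item and then looks for other routes by which the missing content could reach the analysis.

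**Step 1. Items labelled Facilitators/barriers (all first priority).**

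| Content of the prompt | Completers | Drop-outs |
|---|---|---|
| What made use easier | 1 (item 5) | 0 |
| Positive experiences only | 1 (item 6) | 0 |
| Positive or negative experiences | 0 | 1 (item 6) |
| Barriers | 0 | 1 (item 7) |
| Why the person withdrew | 0 | 1 (item 5) |
| Total under the label | 2 | 3 |
| First-priority questions in the guide | 11 | 8 |

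So 2 of the completers' 2 prompts are positively framed and 0 ask for barriers or negative experiences. Of the drop-outs' 3, none asks what made use easier. The only content prompted in both guides is positive experiences.

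**Step 2. Other items in the guides.**
- Both guides open neutrally; the completer version is "Please describe your overall experienced with SENACA".
- Both ask, as the last first-priority item, what should be changed. For completers (item 11) this is "From your perspective what modules, elements etc. should be changed in SENACA in order to improve it".
- Completer item 8 asks about help from other people and is labelled as covering age barriers.
- Both have a second-priority item, "How did you experience the technical support in situations of technical problems", and one on having health data on a computer.
- Drop-outs are asked, at second priority, which element was most useful, which can bring out a driver.

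Difficulties among completers and drivers among drop-outs can therefore surface, but indirectly. Item 11 asks for product changes. It does not directly reach obstacles outside the product, such as time burden, health or circumstances at home.

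**Step 3. Other instruments.** Annex 6 asks about problems in the last 50 days and their frequency (items 8 and 9), and whether and why use was interrupted (item 3a). Only item 10 is reserved for drop-outs. Table 6 schedules errors automatically and at Day 50 and Day 100, and the PSSUQ (Annex 2b) rates error messages and recovery from mistakes. These record the type, frequency and rating of problems and the reason for an interruption. They do not give an account of how a completer coped with an obstacle.

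**Step 4. What the analysis does with the material.** Section 2.2.8 ties barriers and drivers to break-offs and non-response and describes thematic coding of the qualitative data. It states no comparison of completers with drop-outs. If the analysis rests on people who stopped, their guide must supply the drivers and has no direct prompt for what helped. If completers also contribute, their barriers lack a direct prompt. On either reading part of the stated aim is weakly elicited.

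**Step 5. Whether satisfied users report barriers.** The pre-test in section 3 suggests that they do. Its users judged the system positively overall, yet some reported getting lost, scale data that did not transmit, and nutrition entry that took too long. The pre-test guide (Annex 11, question 4) asked directly about problems. The completer guide for the main study has no such question.

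**The case against.** A reader might infer more: that completers are asked only for favourable content, that drop-outs are asked only for barriers, and that any difference between the groups is therefore produced by the questions. The documents do not support this.

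- The completer guide as a whole has a neutral opening, a first-priority question inviting criticism, and an item on technical problems. The one-sidedness is confined to the items under one label.
- Drop-outs are asked for positive experiences as well.
- The interviews are semi-structured and open-ended. Wording steers answers but does not fix them, and nothing in the protocol allows the size of the steering to be estimated.
- Section 2.2.8 plans no contrast between the groups, so there is no planned inference to invalidate.
- Problems and interruptions are also collected by questionnaire. Section 2.2.1 describes a design in which quantitative data come first and weigh more.

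All of this stands, and it limits the point to a risk of under-elicitation. It does not remove the asymmetry itself, because the compensating routes are indirect or record problems without the account that an interview can give.

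It can also be said that use of the elements, behaviour change and self-management have first priority for completers but second priority for drop-outs. That is a defensible choice, since people who stopped early may have little to report, and the topics remain in the guide. It is not part of this point.

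**Conclusion.** The asymmetry is real and can be read directly from Annex 10: 0 of 2 completer prompts under Facilitators/barriers ask for barriers or negative experiences, and 0 of 3 drop-out prompts ask what made use easier. Barriers met by completers and drivers among drop-outs may be under-elicited, and any comparison of the two groups on these themes would be partly confounded with question wording.

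The weight is modest. The study is exploratory and primarily descriptive, the guides are drafts, other items and Annex 6 partly compensate, and no planned test or quantitative outcome depends on these prompts. The conclusion assumes that interviewers follow the guides broadly as written. An interviewer who routinely probes for difficulties would reduce the problem, but the guide does not ask for that.

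**What to change.** Put the same three first-priority prompts, identically worded, in both guides under Facilitators/barriers:
1. Please describe what made it easier for you to use SENACA.
2. Please describe what made it harder for you to use SENACA.
3. Please describe positive and negative experiences with SENACA.

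Keep the question on why the person withdrew as an extra for drop-outs. Leave the priority of the questions on behaviour change, self-management and use of the elements as it is.

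For completers, prompts 1 and 3 replace items 5 and 6 and prompt 2 is new, so 11 first-priority questions become 12. For drop-outs, prompts 2 and 3 replace items 7 and 6 and prompt 1 is new, so 8 become 9. If positive and negative experiences are asked separately, each guide gains two questions instead of one. The cost is thus one or two more questions per phone interview, plus rewording a draft, which is best done before the guides are put into the languages of the three countries.

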### Interview guide for the drop-outs

	First priority questions	Area to cover
Opening question	1 Please describe your overall experience with SENACA?	Overall experience
	2 Please describe your use of computers, mobile devices or other modern electronics in relation to health b using SENACA	Prior ICT experience
Initial experience	3 Describe your thoughts about SENACA when you first heard about it	Technology readiness
	4 Please elaborate on the introduction session giving in advance	SENACA improvements
5 (	5 Please describe the reason(s) why you withdraw from using SENACA?	Facilitators/barriers
Reasons for withdrawing	6 Please elaborate on positive (or negative) experiences produced by using SENACA	Facilitators/barriers
	7 Please describe barriers for you using the program	Facilitators/barriers
Future	8 From your perspective what should be changed in SENACA in order for you to use SENACA?	SENACA improvements
	Second priority questions	
	How did you experience the technical support in situations of technical problems?	SENACA improvements
	Pleace describe your thougths about having your healt data on a computer software	Data security
	Please elaborate on your health behaviour in terms of physical activity, alcohol consumption etc. during th SENACA period	e Behaviour change
	Please elaborate on your level of involvement in managing your health during the SENACA period	Self-management
	Please describe your use of the different elements in SENACA - which one did you find most useful?	SENACA improvements, eHealth literacy
	Please elaborate on your experiences related to the interaction with other people using SENACA (the form	um) Self-management

# 6.15 Annex 11 – Interview guide – usability tests

- 1) What do you think about the usability of the system, the different modules and the devices?
  - a. Triggers: user-friendliness, navigation, steps to accomplish a task
- 2) What do you think about the graphical presentation of the results?
- 3) Is the meaning of the used colors throughout the website clear and easy to understand?
- 4) Have you encountered any problems while using the system? If yes, what kind problems?

# 6.16 Annex 12 – Questionnaire

The following questions are used to evaluate how difficult / easy different areas and tasks of the website were understood.

## How easy was it to setup the SENACA system?

Difficult	0	1	2	3	4	5	Easy

Comments/problems:

### Learning to use the system

Difficu	ılt	0	1	2	3	4	5	Easy

### Comments/problems:

\_

Navigate		within			the			system
	Difficult	0	1	2	3	4	5	Easy

### Comments/problems:

F	Readability		of			content			
	Difficult	0	1	2	3	4	5	Easy	
C	Comments/problems:								

\_

#### It requires the fewest steps possible to accomplish what I want to do with it.

Disagree	0	1	2	3	4	5	Agree

Comments/problems:

Error messages

Unhelpful	0	1	2	3	4	5	Helpful

Comments/problems:

—

### Graphical presentation of the monitoring data (weight, blood pressure etc.)

Confusing	0	1	2	3	4	5	Very clear

Comments/problems:

\_

# It is easy to use the module: Monitoring

Disagree	0	1	2	3	4	5	Agree

Comments/problems:

—

#### It is easy to use the activity tracker.

Disagree	0	1	2	3	4	5	Agree
----------	---	---	---	---	---	---	-------

#### Comments/problems:

—

## It is easy to use the module: Nutrition

Disagree	0	1	2	3	4	5	Agree
Diodgi oo	°	•	-	Ŭ	•	Ŭ	, igi oo

#### Comments/problems:

\_

### It is easy to use the module: Activity

\_\_\_\_\_

Disagree	0	1	2	3	4	5	Agree
----------	---	---	---	---	---	---	-------

#### Comments/problems:

\_

### It is easy to use the module: Health literacy

Disagree 0	1	2	3	4	5	Agree
------------	---	---	---	---	---	-------

### Comments/problems:

\_

### It is easy to use the blood pressure device.

|--|

Comments/problems:

\_

It is easy to use the scale.

Disagree	0	1	2	3	4	5	Agree
----------	---	---	---	---	---	---	-------

Comments/problems:

\_

## It is easy to use the activity tracker.

Disagree	0	1	2	3	4	5	Agree
----------	---	---	---	---	---	---	-------

Comments/problems:

6.17 Annex 13 – Qualcomm 2net Security Q&A

### What is the typical data flow for medical data?

Medical data generated by the medical devices are captured by the Hubs in the homes of the patients, encrypted and transmitted through the cellular networks on the 2net service platform, which for Europe is operated and maintained by Qualcomm IT resources in Amsterdam in the Netherlands. Then the data are collected by the customers and the data are then erased on our Service Platform once we are sure that the customers have correctly collected the medical data.

### *Is there any encryption between measurement device and 2net hub? Bluetooth mode 1,2,3?*

BT 4.0 (BLE) native security supported. End-to-end data encryption from 2net Hub to 2net Service Platform: AES-128 bit encryption.

When is medical data deleted from secure storage after it has been successfully transferred?

Data is deleted automatically after a few days (typically 72-96 hours). Data is maintained temporarily to allow Qualcomm Life (QCL) perform issue troubleshooting and root cause analysis.

### Who is the owner of QCL's data centre in Amsterdam?

The data centre in Amsterdam is co-location and operated by our partner Equinix.

#### Could the US Patriot Act force QCL to give access to patient data under certain circumstances?

Data hosted in EU by QCL is very unlikely to be subject to the U.S. Patriot Act.

- 1. To date, Qualcomm Life, Inc. has never received a request for information pursuant to the USA Patriot Act.
- Qualcomm Life believes it is at very low risk of ever receiving a request from a US official pursuant to the Patriot Act given the nature of the data we process, which is:
   (a) binary data that cannot be read without decoding keys held by the medical device manufacturers,

(b) which binary data is tied solely to medical devices and not specific individuals, even if decoded, and

(c) such binary medical device information is highly unlikely to impact a matter of "foreign intelligence" or "international terrorism" as required for a request under Section 215 of the Patriot Act.

- 3. The 2net data hosted by Qualcomm Life, although not "anonymized" under some countries laws, does not contain information from which without more information from the EU-based client the government would be able to identify any individuals. The only identifiers are device and hub serial numbers. Qualcomm Life does not keep the names associated to the device and hub serial numbers, although the customer may. Without the association, which would have to be provided by an EU customer, the US government would be unable to match any readings to an individual.
- 4. In the highly unlikely event a request was made of Qualcomm Life under the Patriot Act for the 2Net data, Qualcomm Life anticipates it would take the necessary steps to oppose such a request given our position in (2)(c) and 3 above.

